**Table 8.2.1: Visit Window Definition**

Visit	Target Day	Window
Screening	Day -4 to -1	Days < 0
Baseline	Day 1	Days = 1
Week 8	Day 57	Days [1, 85]
Week 16	Day 113	Days [86, 141]
Week 24	Day 169	Days [142, 197]
Week 32	Day 225	Days [198, 253]
Week 40	Day 281	Days [254, 309]
Week 48	Day 337	Days >= 310

### 8.3 Demographics

Summary statistics will be presented for the following variables by treatment group:

- Gender
- Ethnicity
- Race
- Age at diagnosis
- Age at start of treatment
- Height (cm)
- Weight (kg)

### 8.4 Disease Characteristics and Medical History

Summary statistics will be presented for disease characteristics and medical history by treatment group.

### 8.5 Patient Accountability

The number of subjects randomized to each treatment group, included in the primary and safety analysis sets, will be summarized. The reason for treatment discontinuation and study discontinuation will also be summarized by treatment group.

## 8.6 Extent of Exposure

The number of doses, total dose and duration of treatment per patient administered, and dosing compliance will be summarized overall and by treatment group for the Safety Population. Study medication dispensing and treatment compliance will also be listed.

Compliance = total dosage received / total dosage planned \* 100%

## 8.7 Primary Efficacy Endpoint and Analysis

The primary clinical efficacy analysis will be the changes from baseline in UEC score over time for the SA-ER group compared with placebo based on bilateral strength recorded in the following muscle groups using a dynamometer: gross grip, shoulder abductors, elbow flexors, and elbow extensors. The UEC is derived from the sum of the muscle groups. Each muscle group value will represent the average of the right and left total values (measured in kg).

The comparison of the two treatment groups will be based on the changes from baseline over time in mean UEC score between SA-ER and placebo using the week 48 ls-means from GEE repeated measures analysis with baseline, gender, and region as covariates. Region is considered as a covariate to account for the heterogeneity of the disease observed in some European countries and Israel relative to North American patients.

The imputations method described in Section 7.1 will be used to estimate the change in strength for dropouts. Sensitivity analyses will also be performed as described in Section 8.1.

In addition, the primary analysis will be repeated in the Per Protocol population.

## 8.8 Analyses of Secondary and Tertiary Endpoints

Analyses of the secondary and tertiary efficacy variables will follow the same methods as the primary analysis of the primary endpoint. The key and other secondary clinical efficacy analyses will assess the change from baseline to week 48 for the SA-ER group compared with the placebo group using the same methodology as the one for the primary endpoint. Sensitivity analysis will be conducted only for the key secondary endpoints as described in Section 8.1.

### 8.8.1 Analyses of Key Secondary Endpoints

Key secondary endpoints include the following:

- Lower Extremity Composite Score: Muscle strength based on MVIC against a dynamometer will be measured bilaterally in the following lower extremity muscle groups: knee flexors, hip flexors, hip extensors, hip abductors and hip adductors. The LEC is derived from the sum of the average of the right and left raw scores (measured in kg) at each time point through week 48.

- Muscle strength in the knee extensors: bilateral total force (in kg)
- GNEM Functional Activities Scale Mobility Domain score: this is a domain of the GNEM Functional Activities Scale reflective of lower extremity muscle strength

The LEC and Knee extensors will be analyzed in a similar fashion as the primary endpoint including sensitivity analyses as defined in Section 8.1.

Hochberg adjustment for multiplicity (Hochberg 1988) will be used for these three key secondary endpoints.

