7.5.2 Efficacy Measures

Efficacy will be evaluated by changes in upper and lower extremity muscle strength and function, and self-reported physical functioning. Results from baseline assessments will be compared with those of post-treatment assessments listed in the Schedule of Events (Table 2.1), with efficacy conclusions based on change from baseline over the treatment period for the SA-ER treatment group compared to placebo.

The primary efficacy endpoint in this study, UEC as derived from dynamometry, will provide a clinical measure of muscle function and strength. The primary efficacy endpoint will be the change from baseline in UEC score for the SA-ER group compared with placebo based on the overall trend over the treatment period (Section 7.6.4). The primary efficacy measure will be supported by multiple secondary and tertiary endpoints, including GNEM-FAS mobility and upper extremity domain scores, LEC, multiple measures of lower extremity strength and function, clinical performance tests to assess mobility and functional abilities, health-related quality of life assessments, and biochemical markers. Secondary and tertiary endpoints and associated analyses are described in Sections 7.6.4.2 and 7.6.4.3, respectively. The following section describes the assessments that will be performed throughout the study to derive primary, secondary, and tertiary endpoints.

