7.6.4.2.1 Key Secondary Endpoints

The key secondary clinical efficacy analyses will assess the change from baseline for the SA-ER group compared with the placebo group using GEE for the following variables:

- LEC score based on a sum of the mean bilateral strength recorded in the following muscle groups: knee flexors, hip flexors, hip extensors, hip abductors and hip adductors

- Muscle strength in the knee extensors: bilateral total force (measured in kg)
- GNEM-FAS mobility domain score

Hochberg's adjustment for multiplicity (Hochberg 1988) will be used for the key secondary endpoints, specifically LEC score, knee extensor strength, and GNEM-FAS mobility domain score.

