## 8 STATISTICAL METHODS OF ANALYSIS

### 8.1 General Principles

Efficacy analyses will be based on the primary analysis set. GEE analysis ([Hanley et al. 2003](#)) for repeated measures will be performed to compare the two treatment groups with respect to the changes from baseline of primary endpoint, secondary endpoints, and all tertiary efficacy endpoints, using an exchangeable working covariance structure among time points. Baseline, gender and region will be included as covariates in the model. Compound symmetry may be used if convergence is not achieved or if the AIC is larger than the one from the exchangeable covariance structure.

In general, randomly missing efficacy data for an individual subject will be treated as missing. The GEE method might not adequately cover the projected decline for these subjects and may not be appropriately conservative. In such cases a single imputation method will be used to estimate the change in strength over the remaining time of the study as described in [Section 7.1](#) and these imputed values will be used for the GEE analysis. This method of imputation will be the primary analysis method for all repeated measures endpoints.

A sensitivity analysis without use of the single imputation method for dropouts will be also be performed using the same GEE model.

The statistical analyses will be reported using summary tables, figures, and data listings. Statistical tests will be 2-sided at the alpha =0.05 significance level. All analyses and tabulations will be performed using SAS®. Continuous variables will be summarized with means, standard deviations, standard errors, medians, minimums, and maximums. Categorical variables will be summarized by counts and by percentages of subjects in corresponding categories.

The final analysis will be conducted at Week 48.

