### **Hochberg Method for Three Secondary Endpoints**

	p-value	Signif.	p-value	Signif.	p-value	Signif.	p-value	Signif.
Key Secondary Endpoint(1)	≤0.05	Y	>0.05	N	>0.05	N	>0.05	N
Key Secondary Endpoint(2)		Y	≤0.025	Y	>0.025	N	>0.025	N
Key Secondary Endpoint(3)		Y		Y	≤0.0167	Y	>0.0167	N

Key Secondary Endpoints are ranked by p-values from highest to lowest (1 to 2 to 3)

Two sets of analyses will be conducted on the GNEM Functional Activities Scale of Mobility score: one will be on the primary analysis set, and the other will be on the subset of subjects that excludes those subjects with the maximum score at baseline. For example, subjects with score of 40 will be excluded from the analysis of the mobility scale. The same method of analysis model (GEE) as the one for the analysis of the primary endpoints will be used.

In addition, in the subjects with a baseline score less than the maximum of 40, the proportion of subjects in each treatment group who achieve the MID as defined by an increase in Mobility domain score of at least 3.07 points indicating an improvement in mobility or a decrease of at least 3.07 points (GNEM-FAS Dossier) indicating a decline in mobility or changes between -3.07 and 3.07 will also be summarized descriptively as a supportive analysis.

In addition, the cumulative distribution Curve based on change from baseline to Week 48 in FAS mobility will be provided separately in each treatment group.

Analysis of the key secondary endpoints will be repeated in the Per Protocol population.

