#### **8.8.2 Analyses of Other Secondary Endpoints**

No sensitivity analysis will be performed for other secondary endpoints. The rest of the secondary endpoints include changes from baseline to week 48 for the following clinical outcomes:

- GNEM Functional Activities Scale Upper Extremity Domain score: this is a domain of the GNEM Functional Activities Scale reflective of upper extremity muscle strength
- Number of Stands in the Sit-to-Stand Test: Lower extremity function will be assessed using a sit-to-stand test. The number of times the subject can rise from a seated to a standing position in a 30-second period will be recorded.
- Number of Lifts in the 30 second Weighted Arm Lift Test: Upper extremity function will be assessed using a weighted arm lift test performed bilaterally. The number of times the subject can raise a 1 kg weight above the head in a 30-second period will be recorded.
- Meters Walked in the Six-Minute Walk Test: The total distance walked (meters) in a six minute period (6MWT) will be measured as well as the percent predicted distance based on normative data for age and gender.

No adjustment for multiplicity will be performed for these endpoints. Each endpoint will be tested at the 0.05 two sided level of significance and nominal p-values will be reported using the same GEE model as the one for the primary analysis.

Two sets of analyses will be conducted on Functional Activities Scale of upper extremity: one will be on the primary analysis set, and the other will be on the subset of subjects that excludes those subjects with the maximum score at baseline. For example, subjects with a baseline score of 32 in upper extremity will be excluded from the analysis of the upper extremity scale. The same method of analysis model (GEE) as the one for the analysis of the primary endpoints will be used.

In addition, in the subjects with a baseline score less than the maximum of 32 on the GNEM-FAS upper extremity scale, the proportion of subjects in each treatment group who achieve the MID as defined by an increase in UE domain score of at least 1.47 points (GNEM-FAS Dossier) indicating an improvement in UE function or a decrease of at least 1.47 points in UE domain score indicating a decline in UE function or changes between -1.47 and 1.47 will be summarized descriptively as a supportive analysis.

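### Hochberg for the three key secondary endpoints starts at the full two-sided 0.05 with no condition on the primary UEC result, so a key secondary can be declared significant after the primary fails

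*SAP*

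**What the plan says.** SAP 8.1 sets the general level: "Statistical tests will be 2-sided at the alpha =0.05 significance level". SAP 8.7 defines the primary test as the UEC comparison "using the week 48 ls-means from GEE repeated measures analysis with baseline, gender, and region as covariates".

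For the lower extremity composite (LEC), knee extensor strength and GNEM-FAS mobility, SAP 8.8.1 says "Hochberg adjustment for multiplicity (Hochberg 1988) will be used for these three key secondary endpoints". The table that follows ranks the three p-values from largest to smallest, compares them with 0.05, 0.025 and 0.0167, and enters Y or N for significance. It has no row or condition for UEC. Protocol 7.6.4.2.1 has the same scope: Hochberg "will be used for the key secondary endpoints, specifically LEC score, knee extensor strength, and GNEM-FAS mobility domain score".

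For the other secondary endpoints, SAP 8.8.2 says "Each endpoint will be tested at the 0.05 two sided level of significance and nominal p-values will be reported". The key secondaries carry no such label. Protocol 7.5.2 describes the general relationship: "The primary efficacy measure will be supported by multiple secondary and tertiary endpoints".

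The amendment summaries and SAP Appendix 10.7 add no testing order, condition or alpha split. SAP 3.8 plans no interim analysis, so no alpha is spent elsewhere.

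**The concern.** There are two separate chances of a false claim, each at or near 5%: the UEC test, and the Hochberg family of three. Hochberg protects the second but does not link it to the first.

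The case that matters is a failed UEC test with, say, GNEM-FAS mobility at p = 0.01. The SAP table labels mobility significant. The plan does not say whether that label is a claim controlled for multiplicity across the trial's main tests or a nominal finding beneath a failed primary, so the question would be settled with the result already known. Protocol Amendment 5 justifies Hochberg as a way to lower the type I error risk when several hypotheses are tested. Leaving the primary out of the structure achieves that only in part.

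**Working it through.** **Inputs from the documents.** Primary at two-sided 0.05 (SAP 8.1, 8.7). Three key secondaries by Hochberg at 0.05 (SAP 8.8.1; Protocol 7.6.4.2.1). For the cost of a fix: about 80 subjects allocated 1:1, SD 6 kg, planned difference 5 kg, t-test (SAP 3.5, 3.7).

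**The plan's own figures.** Hochberg cut-offs are 0.05/k for k = 1, 2, 3, that is 0.05, 0.025 and 0.0167. The SAP table is correct.

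**Independent tests, no drug effect on any endpoint.** Hochberg rejects nothing if the largest p exceeds 0.05, the middle p exceeds 0.025 and the smallest exceeds 0.05/3. The ways this can happen are:

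- all three above 0.05: 0.95³ = 0.857375
- two above 0.05, one between 0.05/3 and 0.05: 3 × 0.95² × 0.03333 = 0.090250
- one above 0.05, the other two between 0.05/3 and 0.05 but not both at or below 0.025: 3 × 0.95 × (0.03333² − 0.00833²) = 0.002969

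The sum is 0.950594, so Hochberg's own error rate is 1 − 0.950594 = 4.94%. The chance of at least one false claim, primary included, is 1 − 0.95 × 0.950594 = 9.7%. The additive bound is 10%.

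**Correlated tests.** The documents give no correlation between the endpoints. Common values from 0 to 0.9 are assumed; positive values are the more plausible, because three of the four measures are dynamometry in the same subjects. Four equicorrelated normal test statistics were simulated (20 million draws per case), with the primary at 0.05 and Hochberg on the other three regardless of the primary:

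| Assumed correlation | 0 | 0.3 | 0.5 | 0.7 | 0.9 |
|---|---|---|---|---|---|
| Any false claim, two-sided | 9.7% | 9.3% | 8.5% | 7.4% | 5.9% |
| Any false claim favouring the drug | 5.0% | 4.6% | 4.3% | 3.7% | 2.9% |
| Primary fails and a key secondary is falsely claimed | 4.7% | 4.3% | 3.5% | 2.4% | 0.9% |

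The reference is 5% for the first row and 2.5% for the second. Unequal correlations stay within the range. With 0.3 between UEC and each secondary and 0.6 among the secondaries, the two-sided figure is 8.9%; with 0.5 and 0.8 it is 8.0%.

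**If key secondaries are tested only after a significant UEC.** No key secondary claim can then occur without a primary rejection. With no effect anywhere, the chance of any false claim equals the chance that the primary rejects, which is 5.0% at every correlation. The third row becomes zero.

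**If the drug truly affects UEC.** A primary rejection is then not an error, and the only possible false claims are in the Hochberg family. Its own rate is 4.9 / 4.8 / 4.5 / 4.1 / 3.5% at the five correlations, so there is no excess.

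**Cost of the condition.** With 40 per arm, the standard error is 6 × √(2/40) = 1.342 kg. Two-sided t-test power for UEC, and the chance that the key secondaries become nominal, are:

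| True UEC difference | Difference / SE | Power | Primary misses |
|---|---|---|---|
| 5 kg (planned) | 3.73 | 96% | 4% |
| 3.44 kg (Phase 2, Week 48, 6 g versus 3 g) | 2.56 | 72% | 28% |
| 2.33 kg (Phase 2, Week 24, 6 g versus placebo) | 1.74 | 40% | 60% |

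The Phase 2 differences are from Protocol 5.2.3; using SD 6 with them is an assumption.

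**The case against.** The strongest reply is that the benchmark comes from outside the plan. Neither document promises a 5% error rate across UEC and the key secondaries together. The stated aim is an adjustment for the key secondaries, and Hochberg over three endpoints delivers it. This stands: the point is an unstated rule set against convention, not a contradiction or a misuse of Hochberg.

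Second, the hierarchy is partly signalled. There is one primary hypothesis (Protocol 5.4), the secondaries are described as supporting it (Protocol 7.5.2), and SAP 3.3 puts the efficacy evaluation on UEC. That would make a stand-alone claim after a failed UEC harder to defend. It is still a description of roles. The table can be carried out in full without looking at UEC, and the SAP reserves its nominal label for other endpoints.

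Third, the 6% to 10% range is the larger way to express the problem. It is two-sided, and its top end needs zero correlation. For claims favouring the drug the range is 2.9% to 5.0% against 2.5%, and a false key secondary claim alongside a failed primary occurs 0.9% to 4.7% of the time. That is fair, and both sets of figures should be read together.

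Fourth, the condition has a price that depends on the true effect: small at the planned 5 kg, large if the effect is nearer the smaller Phase 2 differences. That also stands and should be weighed openly.

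**Conclusion.** The concern holds. Followed as written, the plan can declare a key secondary significant after UEC fails, and it does not define the standing of that claim. With no effect on any of the four endpoints, the joint two-sided error is about 6% to 10% for common correlations from 0.9 down to 0; only near-perfect correlation brings it lower (5.2% at 0.99). The conclusion rests on normal test statistics, assumed correlations and the conventional joint 5% target. The primary test is unaffected, error within the key secondary family is controlled, and the excess disappears if the drug does affect UEC. The omission is therefore worth correcting but does not threaten the primary result.

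**What to change.** Add to SAP 8.8.1, and repeat in Protocol 7.6.4.2.1:

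*The Hochberg procedure for the three key secondary endpoints is carried out at two-sided 0.05 only if the primary UEC comparison is significant at two-sided 0.05; otherwise their p-values are nominal.*

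This holds the joint error at 5% or less, given independence or positive dependence among the key secondary tests, as Hochberg requires. It costs one sentence in each document and no power for the primary. The price is that no key secondary claim is possible when UEC misses. If the sponsor wants key secondary claims to stand without UEC, the plan should say so before unblinding and state how alpha is divided between the primary and the key secondaries.

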### **Hochberg Method for Three Secondary Endpoints**

	p-value	Signif.	p-value	Signif.	p-value	Signif.	p-value	Signif.
Key Secondary Endpoint(1)	≤0.05	Y	>0.05	N	>0.05	N	>0.05	N
Key Secondary Endpoint(2)		Y	≤0.025	Y	>0.025	N	>0.025	N
Key Secondary Endpoint(3)		Y		Y	≤0.0167	Y	>0.0167	N

Key Secondary Endpoints are ranked by p-values from highest to lowest (1 to 2 to 3)

Two sets of analyses will be conducted on the GNEM Functional Activities Scale of Mobility score: one will be on the primary analysis set, and the other will be on the subset of subjects that excludes those subjects with the maximum score at baseline. For example, subjects with score of 40 will be excluded from the analysis of the mobility scale. The same method of analysis model (GEE) as the one for the analysis of the primary endpoints will be used.

In addition, in the subjects with a baseline score less than the maximum of 40, the proportion of subjects in each treatment group who achieve the MID as defined by an increase in Mobility domain score of at least 3.07 points indicating an improvement in mobility or a decrease of at least 3.07 points (GNEM-FAS Dossier) indicating a decline in mobility or changes between -3.07 and 3.07 will also be summarized descriptively as a supportive analysis.

In addition, the cumulative distribution Curve based on change from baseline to Week 48 in FAS mobility will be provided separately in each treatment group.

Analysis of the key secondary endpoints will be repeated in the Per Protocol population.

#### **8.8.2 Analyses of Other Secondary Endpoints**

No sensitivity analysis will be performed for other secondary endpoints. The rest of the secondary endpoints include changes from baseline to week 48 for the following clinical outcomes:

- GNEM Functional Activities Scale Upper Extremity Domain score: this is a domain of the GNEM Functional Activities Scale reflective of upper extremity muscle strength
- Number of Stands in the Sit-to-Stand Test: Lower extremity function will be assessed using a sit-to-stand test. The number of times the subject can rise from a seated to a standing position in a 30-second period will be recorded.
- Number of Lifts in the 30 second Weighted Arm Lift Test: Upper extremity function will be assessed using a weighted arm lift test performed bilaterally. The number of times the subject can raise a 1 kg weight above the head in a 30-second period will be recorded.
- Meters Walked in the Six-Minute Walk Test: The total distance walked (meters) in a six minute period (6MWT) will be measured as well as the percent predicted distance based on normative data for age and gender.

No adjustment for multiplicity will be performed for these endpoints. Each endpoint will be tested at the 0.05 two sided level of significance and nominal p-values will be reported using the same GEE model as the one for the primary analysis.

Two sets of analyses will be conducted on Functional Activities Scale of upper extremity: one will be on the primary analysis set, and the other will be on the subset of subjects that excludes those subjects with the maximum score at baseline. For example, subjects with a baseline score of 32 in upper extremity will be excluded from the analysis of the upper extremity scale. The same method of analysis model (GEE) as the one for the analysis of the primary endpoints will be used.

In addition, in the subjects with a baseline score less than the maximum of 32 on the GNEM-FAS upper extremity scale, the proportion of subjects in each treatment group who achieve the MID as defined by an increase in UE domain score of at least 1.47 points (GNEM-FAS Dossier) indicating an improvement in UE function or a decrease of at least 1.47 points in UE domain score indicating a decline in UE function or changes between -1.47 and 1.47 will be summarized descriptively as a supportive analysis.

In addition, the cumulative distribution Curve based on change from baseline to Week 48 in FAS UE will be provided separately in each treatment group.

